## 4.1. PRIMARY EFFICACY PARAMETERS

The primary efficacy parameter is progression-free survival (PFS) according to the investigator. RECIST version 1.1 will be used.

Progression-free survival will be calculated from the date of randomisation until the date of progression or death (whatever the reason of death).

The progression-free survival may be censored at the date of last tumour assessment or the date of last contact of a follow-up showing no progression, whichever occurs last, in the following cases:

- On-going patients
- Lost to Follow-Up
- Consent withdrawn
- New Anti Cancer therapy given
- No post baseline assessment
- Adequate assessment no longer available (i.e. non evaluable tumour)
- No baseline assessment.

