(g) Only for patients who discontinued study participation before approval of PA06 :in case of treatment discontinuation for other reason than PD, all efficacy assessments including clinical and biological parameters of bone lesion (described above) must be performed every 6 weeks until disease progression is documented, then survival information will be collected approximately every 6 months until death or end of study. Bone scintigraphy should be performed at any time in case of worsening of at least one of the clinical/biological parameters described above.

(h): If deemed necessary by the investigator ; to be performed on hot spots of bone scintigraphy

(i): Tumour assessment is to be performed every 6 weeks (+/- 3 working days) from randomisation (regardless of the timing of treatment cycles): all lesions found at baseline should be re-investigated at each tumour assessment (for bone lesions, see specific assessment guidelines in Section 8.1.1.2). Additional examinations may be performed if appearance of new lesions is suspected.

(j): Within 72 hours prior to first study drug treatment

(k) Within 2 weeks prior to first study drug treatment

(l) Patients on oral coumarin derivative should have their anticoagulant response (INR) monitored closely

(m) Including evaluation of bone pain, analgesic consumption and assessment of biological parameters (alkaline phosphatases, calcaemia)

(n) to be performed within 24 hours before day 1 of each cycle

(o) if clinically indicated

(p) same than (n) except at cycle 1 day 1

(q) to be known prior to randomisation

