### **Patients randomised in Arm A received:**

- **Vinflunine** at the dose of 280 mg/m^2 on day 1 of each cycle every 3 weeks, over a 20-minute i.v. infusion **and**,

- **Capecitabine** which was self-administered by the patient in an outpatient setting. Patients will take 825 mg/m^2 twice daily per os for 14 consecutive days beginning on day 1 of each cycle followed by 1 week of rest. A cycle of therapy is defined as 3 weeks.

**For patients randomised in Arm B, capecitabine** was self-administered by the patient in an outpatient setting. Patients took 1250 mg/m^2 twice daily per os for 14 consecutive days beginning on day 1 of each cycle followed by 1 week of rest. A cycle of therapy is defined as 3 weeks.

The doses and timing of treatment could be modified based on toxicities experienced by the patient. Dose modifications guidelines are described in Section 5.4 of the protocol.

Patients would continue the study treatment until disease progression, unacceptable toxicity or patient's request.

- Patients showing progressive disease should stop study treatment.
- Patients showing objective response (CR or PR) or stable disease should continue the treatment until progression.

In case of documented progression occurring before the first disease evaluation, the treatment should be discontinued and the response to treatment should be registered as early progression.

After treatment discontinuation, the follow-up period is the time from 30 days after the last study regimen administration or new anticancer treatment start until death.

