### 4. EFFICACY PARAMETERS

Tumour assessment will be performed according to the revised RECIST guidelines (**Eisenhauer E, 2009**). Assessment of all lesions will be carried out at baseline then every 6 weeks (+/- 3 working days) regardless of the timing of the treatment cycles until disease progression.

For patients who discontinued the study treatment before the occurrence of disease progression, clinical and radiological assessments of all lesions will be performed every 6 weeks until disease progression is documented in addition to the survival information. Bone scintigraphy should be performed at baseline and at any time during study in case of suspicion of bone lesions progression due to skeletal related events defined as any observation of the following clinical/biological parameters:

- Pain intensity: increase by at least one grade of the bone related pain using the CTCAE v 3.0 grading:
- Analgesic consumption (per investigator assessment): increase of the analgesic dose by at least 50% or increase of the analgesic level according to the following categories of analgesics: level 1: simple non-opioids analgesic e.g. paracetamol; level 2: weak opioids e.g. codeine or analogs; level 3: strong opioids e.g. morphine.
- Alkaline phosphatase level: increase by at least one grade from baseline or nadir value using the following CTCAE version 3.0 grading.
- Calcaemia: increase by at least one grade from baseline or nadir value using the following CTCAE version 3.0 grading:
- New bone pain symptoms requiring other palliation therapy *i.e.* radiotherapy, surgery, bisphosphonates.
- Spinal cord compression.
- Pathologic bone fracture.

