#### **15.6.2. Date of progression or death**

The date of progression is the first date where PD is assessed. The date used for PFS calculation will be the date of progression or the date of death. Date of first progression or death can be found:

- In CTA module of the CRF,
- In ETA module of the CRF (in case of assessment during the follow-up, i.e. after the end of the treatment period),
- In DRF module of the CRF in case of death without “objective” progression assessed before.

If for a tumour evaluation, several assessments show a PD at different dates and the global response of the cycle is PD, the minimum of all the dates of assessment of the cycle showing PD (including appearance of new lesions) will be taken into account.

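### SAP 4.1 censors PFS for new anticancer therapy but does not cap the censoring date at the start of that therapy, and leaves open whether later progression or death is an event

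*SAP*

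**What the plan says.** SAP 4.1 runs PFS from randomisation to progression or death from any cause. It then provides, with the permissive verb *may*, for PFS to be treated as "censored at the date of last tumour assessment or the date of last contact of a follow-up showing no progression, whichever occurs last". Seven cases are listed, among them "New Anti Cancer therapy given" and "No post baseline assessment". One date rule serves all seven, and no start date is attached to the new-therapy case.

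Other places provide for data after a switch:

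- SAP Section 2: "the follow-up period is the time from 30 days after the last study regimen administration or new anticancer treatment start until death". Follow-up can therefore begin on the day new therapy starts.
- SAP Section 4, for patients who stop treatment without progression: "clinical and radiological assessments of all lesions will be performed every 6 weeks until disease progression is documented".
- Protocol Table 1, footnote (g), for those who discontinued before amendment PA06: efficacy assessments "must be performed every 6 weeks until disease progression is documented".
- SAP 15.6.2 takes the first progression date from several CRF modules. One source is given as "In ETA module of the CRF (in case of assessment during the follow-up, i.e. after the end of the treatment period", with no condition about new therapy.

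SAP 10.1 reports PFS by arm with a stratified Cox hazard ratio, 95% confidence interval and Kaplan-Meier curves, and excludes testing. SAP 10.2 rules out sensitivity analyses of PFS.

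**The concern.** PFS is censored at new therapy so that outcome on a different drug is not attributed to the randomised arm. That works only if the censoring date falls on or before the switch. Here the date is the later of two dates, and either can fall well after it. A patient censored for new therapy can then contribute progression-free time on the new drug, while the progression that ends that time is not counted.

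The permissive verb, set against the any-cause event definition in 4.1 and the follow-up sources in 15.6.2, also leaves the status of later events open. Two programmers could follow this SAP and report different medians and hazard ratios. PFS is the only efficacy result left in the report, and no planned table or curve would show which choice was made.

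**Working it through.** **The plan's own figure.** Schoenfeld events at HR 4.0/5.5 = 0.727, two-sided 5%, 80% power: 4 × (1.960 + 0.842)² / (ln 0.7273)² = 31.4 / 0.1014 ≈ 310, as stated in SAP Section 3. The point below does not change it.

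**One patient, using the duration formula in SAP 15.1**, (Date 2 − Date 1 + 1) / 30.4375. Days are counted from randomisation. The patient stops without progression on day 63, starts new therapy on day 70, has clean scans on days 42, 84, 126 and 168, and has progression found on day 210.

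- Date capped at new therapy: censored on day 42, (42 + 1)/30.4375 = 1.41 months.
- Censored for new therapy at the SAP 4.1 date: day 168, (168 + 1)/30.4375 = 5.55 months. That is 4.14 months more, with three of the four scans on the new drug.
- Progression found in follow-up counted under 15.6.2: an event on day 210, (210 + 1)/30.4375 = 6.93 months.

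The same record therefore gives 5.55 months censored or 6.93 months with an event under the present text.

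**Group level.** Inputs from the documents: control median 4.0 months, scans every 42 days, 35 cycles (735 days) as the limit. Assumptions: true HR 1.0, exponential progression times, switching independent of prognosis, hazard unchanged after the switch, and the share of patients switching before detected progression. The simulation used 400,000 patients per arm, Cox HR with Efron ties and medians interpolated between scans.

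| Switching A v B (assumed) | Handling of switchers | HR | Medians, months |
|---|---|---|---|
| 20% v 10% | date capped at new therapy | 1.00 | 4.0 v 4.0 |
| 20% v 10% | SAP 4.1 date, scans to progression, later event not counted | 0.90 | 4.40 v 4.17 |
| 20% v 10% | as above, at most one scan after the switch | 0.97 | – |
| 20% v 10% | later progression counted as an event | 1.00 | 4.0 v 4.0 |
| 10% v 20% | SAP 4.1 date, scans to progression, later event not counted | 1.11 | – |
| 10% v 5% | same | 0.96 | – |
| 20% v 20% | same | 1.00 | about 4.4 in both |

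Equal switching leaves the hazard ratio alone only when the arms do not differ. In a separate run that dated progression exactly, a true HR of 0.727 with 20% switching in each arm became 0.77.

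**Scale.** With 112/2 = 56 patients per arm, 10% is about 6 patients and 20% about 11. At an assumed 80 events, the 95% confidence interval spans a factor of exp(1.96 × 2/√80) = 1.55 either side of the estimate, more than any shift in the table.

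**The case against.** The strongest reply is that the harmful result follows from only one reading. SAP 4.1 counts death whatever its cause, 15.6.2 accepts progression found in follow-up, and censoring is only permitted. If every event counts and the last clean date censors only patients without an event, the uncapped date is coherent and the simulated hazard ratio stays at 1.00. This stands. A reader might infer that the plan as written biases PFS, or that it favours the combination arm; the documents support neither. They give no switching rates by arm, and the shift can go either way. The reply does not remove the problem, however: on that reading, listing new therapy as a censoring reason does almost nothing, and the text does not say which reading applies.

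Three further points stand. The 0.90 figure is an upper-end value that needs scanning to continue until progression on another drug. PA06 ended follow-up assessments, so the patients concerned are mainly those who stopped before it. The Protocol synopsis calls the results exploratory. Dates could also be re-derived from the listings in SAP Appendix 1 (16.2.6), although the reported median and curve would not reveal the effect. Only the synopsis and flow chart of the protocol were supplied, so a limit in its main body cannot be excluded.

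It is also tempting to say that patients without a baseline or post-baseline scan gain unscanned progression-free time. That holds only if a follow-up contact without a scan qualifies under 4.1, which the wording does not settle.

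**Conclusion.** The gap in the text is real. A stated censoring reason carries a date that can fall after the event it is meant to censor for, and the status of later progression or death is undefined. The bias is conditional: it arises if new therapy is applied as a censoring reason with this date and the later event is dropped. In that case medians rise (from 4.0 to about 4.2 months at 10% switching and about 4.4 at 20%). With no true difference, the hazard ratio moves in favour of the arm with more switching, by about 3% to 10% at 20% v 10%, depending on how long scanning continues. Those shares, the 80 events and independence of switching from prognosis are assumptions; size and direction in the 112 patients cannot be derived from the documents. Because the analysis is descriptive and the shifts lie within its uncertainty, no test, error rate or power claim is affected. This is a minor to moderate correction, worth making because the point estimates are the whole efficacy result.

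**What to change.** Rewrite the rule in SAP 4.1 and align 15.6.2 with it:

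- Change *may be* to *will be*.
- Keep the plan's choice to censor for new therapy, but date it at the last evaluable tumour assessment showing no progression on or before the start of that therapy.
- State that progression or death on or before that start is an event. This includes the case in SAP Section 2 where "the response to treatment should be registered as early progression". Progression or death first recorded after that start is not an event in this analysis.
- Date the other censored cases by the last evaluable tumour assessment rather than by a contact without a scan. Without a baseline or post-baseline assessment, censor at randomisation.
- Because patients may switch when progression is near, capping can censor informatively. Show beside it PFS counting every progression and death regardless of new therapy, and amend 10.2 to allow this.

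The cost is one paragraph, one changed derivation and one extra display. It uses scan dates and the new-therapy start date, on which SAP Section 2 already relies. Reported medians may be slightly shorter, and a few events after new therapy leave the main analysis.

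### SAP 4.1 lets PFS be censored at a follow-up contact with no tumour assessment behind it, so the reported median PFS can stay the same or rise, but cannot fall

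*SAP*

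**What the plan says.** SAP 4.1 defines investigator-assessed PFS from randomisation to progression or death and states that "RECIST version 1.1 will be used". For a patient without an event, the rule permits (but does not require) censoring at the last tumour assessment or "the date of last contact of a follow-up showing no progression, whichever occurs last".

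The cases listed under that rule include "Lost to Follow-Up", "Consent withdrawn", "No post baseline assessment" and "Adequate assessment no longer available (i.e. non evaluable tumour", together with patients lacking a baseline assessment. Ongoing patients and "New Anti Cancer therapy given" fall under the same rule. Whether time after a new therapy should count is a separate question and is not taken up here.

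Three other places bear on the point:

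- SAP 1 makes the median PFS in the ITT population the primary efficacy result. SAP 10.1 adds a stratified Cox hazard ratio with its confidence interval and no test. SAP 10.2 rules out sensitivity analyses.
- SAP 15.6.2 takes the progression date from an assessed PD, in the on-treatment or follow-up tumour module, or else uses death.
- The protocol synopsis (End of study) ends all follow-up assessments once PA06 is approved. Flow-chart note (d) puts the end-of-treatment visit 30 ± 3 days after discontinuation. Note (g), attached to the imaging at that visit, applies only to patients who discontinued before PA06.

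**The concern.** The rule names the contact separately from the tumour assessment and lets the later date win. It does not say how a contact shows absence of progression when no scan was done. Read with SAP 15.6.2, the rule is one-sided: a contact without an assessment can lengthen progression-free time but cannot produce a progression event.

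The strength of the point differs by group. With no baseline scan, no post-baseline scan, or a tumour that can no longer be evaluated, no adequate RECIST comparison can exist at the later date. A patient who is lost or withdraws may or may not have been scanned at her last contact. A patient who stops treatment after PA06 for a reason other than progression can have an end-of-treatment contact for which no imaging is required.

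What is at stake is the accuracy of the main reported number. As planned, no second analysis would show how far it depends on the rule.

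**Working it through.** **1. The plan's own figure.** SAP 3 gives 310 events for HR 0.727, two-sided α = 0.05 and 80% power. With 1:1 allocation the Schoenfeld formula is D = 4(z₀.₉₇₅ + z₀.₈₀)² / (ln HR)². The numerator is 4 × (1.960 + 0.842)² = 31.40. At HR 0.727, (ln HR)² = 0.1017 and D = 309. At HR = 4.0/5.5, (ln HR)² = 0.1014 and D = 310. The figure reproduces and is not affected by this point.

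**2. Direction.** The Kaplan-Meier estimate is S(t) = ∏(1 − dⱼ/nⱼ) over event times tⱼ ≤ t. Moving a censoring date later adds no event (dⱼ is unchanged) but raises nⱼ at every event time in between. Each factor stays the same or grows, so the curve is never lower and the median never earlier. This needs no assumption.

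**3. The gap the schedule allows.** Scans are every 6 weeks (42 days), and the end-of-treatment contact falls 27–33 days after discontinuation. If no scan was missed and none is done at that visit, the contact comes between 27 days (3.9 weeks) and 33 + 42 = 75 days (10.7 weeks) after the last scan. The midpoint is 51 days (7.3 weeks). Counted from leaving scanning rather than from the last scan, the gap is about 33 days (1.1 months), or 45 days (1.5 months) with some slack.

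**4. Size for the median.** Inputs from the documents: 112 patients, 1:1 allocation, planned medians of 4.0 (control) and 5.5 months (arm A), scans every 6 weeks. Assumptions: 56 patients per arm, exponential PFS, scan dates ±4 days, no deaths apart from PFS events, 10–30% of patients going off assessment at a uniform time in months 0–6, and a fixed gap from last scan to contact. Each simulated trial was analysed under both censoring dates. Mean rise in the median with last-contact rather than last-scan censoring, in months (control / arm A):

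| Patients affected | 3-week gap | 6-week gap | 12-week gap |
|---|---|---|---|
| 10% | 0.04 / 0.05 | 0.09 / 0.14 | 0.19 / 0.26 |
| 20% | 0.10 / 0.13 | 0.20 / 0.23 | 0.44 / 0.54 |
| 30% | 0.18 / 0.21 | 0.36 / 0.46 | 0.65 / 0.87 |

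The median fell in no run. The midpoint gap of 7.3 weeks lies nearest the 6-week column. With the gap counted from leaving scanning (up to 33–45 days) and 10–30% of patients affected, the control-arm rise is about 0.1–0.4 month.

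The rise can also be zero. If all scans fall exactly on the 6-week grid and the contact precedes the next scheduled scan, the median did not change in any of 1,000 runs (gaps of 3 and 5 weeks, 20% affected). On the same grid it rose by 0.22 month on average at 7 weeks and 0.41 at 12 weeks.

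**5. Which date is closer to the truth.** With a true control median of 4.0 months, complete scanning gives an observed median of about 4.7 months, because PD is dated at the next scan. Last-scan censoring gives 4.6–4.8. The rise under last-contact censoring is therefore error, not a correction.

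**6. Hazard ratio.**

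- *Balanced loss:* with 20% affected in each arm, a 12-week gap and true HR 0.727, it is 0.725 under both rules.
- *Unequal loss, short gap:* with 20% (A) v 10% (B) and true HR 1, it is 1.01 (contact), 1.04 (last scan) and 1.02 (complete scanning) for contacts up to 33 days after leaving. For contacts up to 45 days the values are 0.99, 1.02 and 1.01.
- *Unequal loss, long gap:* with 30% (A) v 10% (B), 12 weeks and true HR 1, it is 0.94 (contact) v 1.02 (last scan). With the shares reversed it is 1.05 v 0.97.

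**The case against.** The best defence is a narrower reading. SAP 4 describes assessment before progression, for patients off treatment, as clinical and radiological assessment every 6 weeks, and SAP 15.6.2 keeps follow-up assessments in their own CRF module. The rule could then mean the later of the last on-treatment and the last follow-up tumour assessment. That reading is possible for some patients. It does not fit those with no baseline or no post-baseline assessment, whom the same rule covers, nor the end-of-treatment visit after PA06, where imaging is not required. If it was intended, the SAP should say so.

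Second, the consequence is limited. The results are declared exploratory, and tumour assessments and PFS will be listed by patient, so last-scan censoring could be recomputed. The sampling standard error of a median from 56 patients is roughly 0.8 month, larger than the shift. All of this stands. But the shift has one direction, the confidence interval does not reflect it, and few readers will rebuild the result from listings.

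Third, the simulations leave out death after scanning stops. Simply counting every later death while dropping the same interval for survivors makes inclusion depend on outcome. With an assumed death hazard of 10% per month after leaving and contacts up to 6 months later, that simple repair gave HR 1.05, against 0.99 under the SAP rule and 1.01 with complete scanning. This also stands, and it shapes the fix.

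A reader might also infer that the rule could make an ineffective combination look active. With 20% v 10% leaving scanning, no true difference and contacts up to 6 months later, the simulated HR is 0.92 v 1.01 with last-scan censoring, and the arm A median is 5.4 v 4.7 months. The documents do not support such gaps as typical. Flow-chart notes (f) and (g) set 6-weekly assessment until progression and 6-monthly contact only afterwards, and PA06 stops follow-up. Nor do they support the inference that lost or withdrawn patients necessarily lack a scan at last contact.

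**Conclusion.** The point holds as a defect in the censoring rule. That the median stays the same or rises follows from the estimator. The size, roughly 0.1–0.4 month per arm, rests on assumed shares of 10–30% and on contacts up to about 1–1.5 months after leaving scanning. It would be larger if visits were missed for longer. For comparison, the planned difference was 1.5 months.

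The hazard ratio shifts materially only when gaps are long and loss is unequal, and then in favour of the arm that loses more patients. The documents do not show that either condition is met. Because no test is planned, the effect is on the reported median, curve and hazard ratio. The change is worth making because it is cheap and because no planned analysis would otherwise reveal the dependence.

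**What to change.** Replace the permissive later-of-two-dates rule in SAP 4.1 with fixed wording, for example:

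*A patient without progression or a countable death will be censored at her last evaluable RECIST 1.1 tumour assessment without progression, or at day 1 if she has no baseline or no post-baseline assessment. Death counts as an event if no more than a stated number of scheduled 6-weekly assessments (for example, two) were missed before it; otherwise the same censoring dates apply.*

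The limit on missed assessments keeps late deaths from being counted while the same interval is dropped for survivors. Making the rule mandatory also removes discretion over the date in an open-label trial.

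Amend SAP 10.2 to report last-contact censoring as a sensitivity analysis, and give the number of patients per arm whose two dates differ, with the gap.

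The cost is a short SAP edit, a small change to the derivation and one extra table. No new data are needed. The stated medians may be slightly less favourable, and a little follow-up time is lost.
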